5. STATISTICAL ANALYSES

5.1 GENERAL CONSIDERATION

All virology and efficacy analyses will be performed on the mITTi population.

All primary and secondary virology endpoints will be produced using the nasopharyngeal swab samples. Additional descriptive analyses for saliva and serum samples will be performed on an exploratory basis for the primary and secondary virology endpoints, as required. A summary of the sampling differences between cohorts is provided in [Table 3](#). Refer to Appendix 1 and Appendix 2 of the study protocol for further details.

No alpha adjustments for multiple comparisons are planned.

For all cohorts, the primary virology analysis will be performed as part of a Day 10 Review (accompanied with key safety review if deemed necessary, see [Section 5.7.1](#)) which is to be completed after all patients enrolled in the current cohort have completed assessments through Day 10. Other endpoints will be analyzed at the completion of each full cohort or at the completion of the study. All analyses at the Day 10 review or at the completion of each cohort will compare each AT-527 dose group and a combined placebo group, including all placebo patients enrolled across cohorts up to the cohort being analyzed, while analyses performed at the completion of the study will compare each AT-527 dose group and a combined placebo group from all cohorts.

Table 3 Differences in Virology Sampling Between Cohorts

Assessment	Cohort A	Cohorts B–E
Nasopharyngeal swab sample for COVID-19 virology	Once a day on Days 1, 3, 5, and 7	Once a day on Days 1, 3, 5, and 7
Saliva sample for COVID-19 virology	NA	Once a day on Days 1, 3, 5, and 7
Serum sample for anti-SARS-CoV-2 antibodies and viral RNA	Once a day on Days 1 and 7	Once a day on Days 1, 3, 5, and 7

COVID-19 = coronavirus disease 2019; NA = not applicable; SARS-CoV-2 = severe acute respiratory syndrome coronavirus-2.

For virology endpoints, the time windows for each assessment are given in [Table 4](#). The time windows will be used for all virology endpoints except the time-to-event endpoints.

Table 4 Virology Assessment Time Windows

Scheduled Timepoint ^{a, b, d}	Acceptable Time Window
Baseline (Day 1 pre-dose)	Day 1 pre-dose ^c
Day 3	Day 2 – Day 3
Day 5	Day 4 – Day 5
Day 7	Day 6 – Day 8

^a An unscheduled visit represents a visit that is not specified by the protocol but is determined to be necessary by the investigator or Sponsor (e.g., for evaluation of an adverse event). Assessments (including PK sample collection) should be performed as clinically indicated. For unscheduled visits occurring after Day 7, PK sample collection is not required.

^b Patients who discontinue study drug prematurely will continue to complete assessments as indicated until the end of the study. Patients who discontinue from study participation will have an early termination visit 7 (\pm 2) days after their final dose of study drug. Patients who discontinue from the study after Day 14 will not be required to complete an early termination visit.

^c If no pre-dose sample is available, a sample taken up to 2 hours post-dose can be used as baseline.

^d No unscheduled visit or early termination serum sample to be taken for Cohort A.

For vital signs, including oxygen saturation, the time windows for each assessment are given in [Table 5](#).

Table 5 Vital Signs (Including Oxygen Saturation) Time Windows

Scheduled Timepoint ^{a, b, d}	Acceptable Time Window
Baseline (Day 1 pre-dose)	Day 1 pre-dose ^c
Day 3	Day 2 – Day 3
Day 5	Day 4 – Day 5
Day 7	Day 6 – Day 8

^a An unscheduled visit represents a visit that is not specified by the protocol but is determined to be necessary by the investigator or Sponsor (e.g., for evaluation of an adverse event).

Assessments (including PK sample collection) should be performed as clinically indicated.

For unscheduled visits occurring after Day 7, PK sample collection is not required.

^b Patients who discontinue study drug prematurely will continue to complete assessments as indicated until the end of the study. Patients who discontinue from study participation will have an early termination visit 7 (± 2) days after their final dose of study drug. Patients who discontinue from the study after Day 14 will not be required to complete an early termination visit.

^c Baseline is defined as the last assessment prior to treatment.

^d These time windows do not apply to temperature. Temperature is collected as part of the COVID-19 Symptom Diary (twice a day on Days 1–14; once a day on Days 15–28).

For lab parameters (hematology, chemistry), the time windows for each assessment are given in [Table 6](#).

Table 6 Laboratory (Hematology, Chemistry) Time Windows

Scheduled Timepoint ^a	Acceptable Time Window
Baseline (Day 1 pre-dose)	Day 1 pre-dose ^b
Day 3	Day 2 – Day 4
Day 7	Day 5 – Day 9

^a An unscheduled visit represents a visit that is not specified by the protocol but is determined to be necessary by the investigator or Sponsor (e.g., for evaluation of an adverse event).

Assessments (including PK sample collection) should be performed as clinically indicated.

For unscheduled visits occurring after Day 7, PK sample collection is not required.

^b Baseline is defined as the last assessment prior to treatment.

Unscheduled visit and early termination visit data will also be mapped according to the acceptable time windows per [Table 4](#), [Table 5](#), and [Table 6](#). Where multiple measurements within a visit window are available for a patient, the value obtained closest to the target timepoint (center of the acceptable time window) will be used. If two measurements collected with the same time deviation exist before and after the target timepoint, the measurement obtained before the target timepoint will be adopted for analysis. However, preference will always be given to measurements collected on the day specified in the scheduled timepoint. The assessment timepoint having no

measurements within the corresponding acceptable time window will be considered as missing and will not be included in the analysis for the timepoint in question.

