5.4 SECONDARY ENDPOINTS ANALYSES

All secondary endpoints will be analyzed descriptively and summary statistics will be presented. Descriptive comparisons will be made for each AT-527 group and a pooled placebo group containing patients from all cohorts. For time to event endpoints, a Kaplan-Meier plot and the median time to response will be presented along with the 80% CI. For proportion, frequency and incidence endpoints, the number, proportion and difference in proportions along with 80% CIs will be presented. For area under the curve (AUC) endpoints, summary statistics will be presented.

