5.5 EXPLORATORY ENDPOINTS ANALYSIS

Exploratory Virology Endpoint Analyses

The following virology exploratory endpoints will be compared between each AT-527 dose group and the pooled placebo group:

- Treatment-emergent amino acid substitutions in SARS-CoV-2 viral genes (nsp12 and potentially other genes)
- Anti-SARS-CoV-2 antibody status/titer at specified timepoints
- Change from baseline in SARS-CoV-2 virus titer at specified timepoints
- Time to cessation of SARS-CoV-2 viral shedding as measured by virus titer
- Proportion of patients with positive SARS-CoV-2 virus titer at specified timepoints
- AUC of SARS-CoV-2 virus titer
- Drug susceptibility in patients with evaluable virus at specified timepoints

Polymorphic and treatment-emergent substitutions in nsp12 and potentially other genes will be reported descriptively, and the percentage of patients with those viral mutations will be calculated.

Exploratory endpoints defined by virus titer will be summarized using descriptive statistics similar as specified for the secondary endpoints defined by SARS-CoV-2 virus RNA.

Drug susceptibility will be reported as EC₅₀ values, and respective fold-change values (ratio of EC₅₀ sample / EC₅₀ reference) will be calculated from those. A summary of drug susceptibility with summary statistics will be produced at baseline (and other timepoints, if required), together with an individual patient listing of drug susceptibility.

Exploratory Pharmacokinetic Endpoint Analyses

The exposure-response profile of AT-511 and its major metabolites will be explored (e.g., relationship between plasma concentration of AT-273 and antiviral activity) and will be reported in a standalone document separate from the CSR.

Respiratory Coinfections (Biofire)

All baseline (nasopharyngeal) samples will be tested for respiratory pathogens using the qualitative PCR-based FDA cleared BioFire FilmArray® Respiratory Panel 2 assay. This

assay detects 19 respiratory viral or bacterial pathogens. Frequency and proportions for each co-infection will be presented.

Exploratory Patient Global Impression of Severity Endpoint

The exploratory endpoint to evaluate patients' self-assessment of COVID-19 symptom severity as assessed by Patient Global Impression of Severity (PGIS) at Days 14 and 28 will be summarized using mean scores on a 4-point Likert scale: "none" (0) to "severe" (3).

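### Serum time to clearance, and under some curve shapes serum AUC, will differ between AT-527 and pooled placebo by sampling schedule alone, because Cohort A has serum only on Days 1 and 7

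*SAP*

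**What the plan says.** **Schedule.** SAP Table 3 sets Cohort A serum at "Once a day on Days 1 and 7" and the later cohorts at "Once a day on Days 1, 3, 5, and 7". Protocol Appendices 1 and 2 agree for Cohort A and Cohorts B–D. A footnote to SAP Table 4 closes off any extra samples: "No unscheduled visit or early termination serum sample to be taken for Cohort A".

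**Placebo group.** SAP 5.1 makes the comparator for all analyses a combined placebo group, "including all placebo patients enrolled across cohorts up to the cohort being analyzed". At study end it is the placebo group from all cohorts. SAP 5.4 repeats this for secondary endpoints: "Descriptive comparisons will be made for each AT-527 group and a pooled placebo group containing patients from all cohorts". SAP 5.5 does so for antibody status and the other exploratory virology endpoints: "The following virology exploratory endpoints will be compared between each AT-527 dose group and the pooled placebo group". There is no exception for serum.

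**Endpoints.** SAP 5.1 and 5.4.2.1 base the primary and secondary virology endpoints on the nasopharyngeal swab, and also allow serum versions. In the words of 5.1: "Additional descriptive analyses for saliva and serum samples will be performed on an exploratory basis for the primary and secondary virology endpoints, as required". In 5.4.2.1, time to cessation of shedding runs to the first negative or below-quantification result, and sustained non-detectability requires in addition no later quantifiable result. Both are summarised by Kaplan-Meier curves and medians. AUC is a trapezoid over the assessments, and missing data are left out.

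**The concern.** A time to first negative sample depends on when samples are taken. A Cohort A patient has one post-baseline serum sample, on Day 7; a Cohort B–D patient has three. Two patients who clear serum RNA on Day 2 are recorded at Day 3 in Cohorts B–D and at Day 7 in Cohort A. Pooling their placebo groups therefore mixes two measurement scales, while each AT-527 group sits on only one of them. Table 3 lists the sampling difference, but the analysis text does not act on it. Following the plan as written gives a serum clearance curve that favours AT-527 in Cohorts B–D and disfavours it in Cohort A at study end, whatever the drug does.

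**Working it through.** **Inputs from the documents.** Cohort A: 60 patients at 1:1, so 30 placebo. Each of Cohorts B–D: 40 at 3:1, so 10 placebo (SAP 3, Protocol 6.1). Days 3, 5 and 7 are taken as 48, 96 and 144 h after first dose.

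**The plan's own figure.** The documents give no figure for serum. The arm sizes behind this check do reproduce: at 27 per arm and one-sided 10% alpha, t-test power is 80.1% for 0.7/1.2 and 81.2% for 1.1/1.85, and 27/0.9 = 30. The sample size is not at issue.

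**Make-up of the pooled placebo group.**
- At Cohort B: 30 of 40 from Cohort A = 75%; 10 have Day 3 and Day 5 serum.
- At Cohort C: 30 of 50 = 60%; 20 have them.
- At Cohort D: 30 of 60 = 50%; 30 have them.

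**Time to clearance, no drug effect.** The documents give no serum clearance times, so exponential clearance with median m is assumed, the same in both arms, over a range of m. The fraction cleared by time t is F(t) = 1 − 2^(−t/m).

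Mean recorded time up to 144 h on the fuller schedule: R = 48·F(48) + 96·[F(96) − F(48)] + 144·[1 − F(96)]. On the Cohort A schedule it is 144 h for everyone.

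For m = 72 h: F(48) = 0.370, F(96) = 0.603, F(144) = 0.750.
- R = 17.8 + 22.4 + 57.2 = 97 h.
- Pooled placebo at Cohort B: 0.75 × 144 + 0.25 × 97 = 132 h. At Cohort D: 0.50 × 144 + 0.50 × 97 = 121 h.
- Median for AT-527 in Cohort B: F passes 0.5 between 48 and 96 h, so it is recorded as 96 h.
- Median for pooled placebo: only 0.25 × 0.603 = 0.15 (Cohort B) or 0.50 × 0.603 = 0.30 (Cohort D) are recorded as clear by 96 h, so it is 144 h.
- Clear by Day 7: 0.75 in both arms.

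| Assumed true median | AT-527, fuller schedule: mean | Pooled placebo at B: mean | Pooled placebo at D: mean |
|---|---|---|---|
| 48 h | 84 h | 129 h | 114 h |
| 72 h | 97 h | 132 h | 121 h |
| 96 h | 106 h | 134 h | 125 h |

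Simulation with 27 AT-527 patients against 27 + 9 (Cohort B) or 27 + 27 (Cohort D) placebo patients gave the same values to within about 1 h. With placebo on the same schedule, the arms agreed within about 1 h.

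**Reverse direction.** Cohort A AT-527 reads 144 h throughout. Against the final A–D pool at m = 72 h that is 144 h versus 121 h, with no true difference.

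**If serum is negative throughout.** The analysis population is defined by swab (SAP Table 2), so serum-negative patients stay in and clear at their first post-dose sample. Cohort B AT-527 then reads 48 h. Pooled placebo has a mean of 0.75 × 144 + 0.25 × 48 = 120 h and a median of 144 h.

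**AUC, no drug effect.** Assumed log10 curves at 0, 48, 96 and 144 h, floor log10(60) = 1.778:
- Straight line or flat: two- and four-point trapezoids agree, difference 0%.
- Early fall (4, 2.5, floor, floor): four points 48 × 7.167 = 344; two points 144 × 5.778/2 = 416. Pooled placebo is 398 at Cohort B (+16%) and 380 at Cohort D (+10%).
- Rise then fall (3, 3.5, 2.5, floor): 403 against 344. Pooled placebo is 359 at Cohort B (−11%) and 373 at Cohort D (−7%).

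**By-visit summaries.** Serum change from baseline, proportion positive and antibody status compare patients sampled on the same day. On Days 3 and 5 the placebo group is Cohorts B–D only, so n falls, but no value is moved by the schedule.

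**The case against.** The strongest reply is that nothing important rests on this. Serum versions are descriptive, exploratory and produced only if required. Swabs are taken on Days 1, 3, 5 and 7 in every column of Table 3. The Day 10 Review in SAP 5.7.1 names swab, saliva and virus titer, not serum RNA, and dose decisions for Cohorts C–D follow safety review. All of this stands, and it limits the point to a minor one. It does not remove the artefact, because a misleading median or curve needs no test to appear.

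A reader might infer more than the documents support:
- *That the trial's false-positive rate is inflated.* In the simulations a one-sided 10% log-rank on serum clearance would favour drug in 55–96% of null trials at Cohort B and 38–83% at Cohort D, for medians of 96 down to 48 h with every patient viraemic. But no serum test is planned. SAP 5.4.1 only permits tests for secondary endpoints, which are swab-based. These rates measure the bias and are not operating characteristics of the study.
- *That antibody comparisons are biased.* They are made at matched visits. A placebo trend across days could move through the change of patients, but only if cohorts differ in serostatus, and the documents give no such figure.
- *That serum AUC favours AT-527.* It can go either way or not differ at all. It also presupposes that two-point Cohort A curves are kept, which the missing-data wording does not settle.

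**Conclusion.** The point holds for serum time to clearance. With identical clearance in both arms, the plan as written yields a Kaplan-Meier median of about 96 h for Cohort B AT-527 against 144 h for pooled placebo, at an assumed true median of 72 h. The gap in mean recorded time at Cohort B is 28 to 45 h for medians of 96 down to 48 h. It shrinks as Cohort A's share of placebo falls from 75% to 50%, and it reverses for Cohort A AT-527 against the final pool. The size rests on assumed clearance times and serum positivity. The direction follows from the schedules and the first-negative definition. For serum AUC the point is conditional on curve shape and on how two-point curves are treated. Primary and secondary swab endpoints, and by-visit serum and antibody comparisons, are not biased by the schedule. Severity: minor.

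**What to change.** In SAP 5.1 and 5.4.2.1, state that serum time to clearance and serum AUC compare each AT-527 group only with placebo on the same serum schedule: Cohort A with Cohort A, Cohorts B–D with Cohorts B–D. Alternatively, use only Days 1 and 7 from every cohort whenever placebo is pooled; clearance then reduces to the proportion negative at Day 7. Either rule removes the artefact. Keep pooled placebo for by-visit serum RNA and antibody summaries, and show n at each visit.

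Also align Table 3 with Protocol Appendix 3. The table puts Cohort E with the later cohorts on Days 1, 3, 5 and 7, whereas Appendix 3 gives Cohort E serum on Days 1, 7 and 14, and Protocol 6 keeps Cohort E out of the pool.

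The cost is wording, plus a smaller placebo group for these two exploratory summaries under the same-schedule option: 10 instead of 40 at Cohort B, 20 instead of 50 at C, and 30 instead of 60 at D. No sampling or sample size changes.

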6. STATISTICAL CONSIDERATIONS AND ANALYSIS PLAN

All primary and secondary virology and efficacy outcomes will be analyzed in the modified intent-to-treat infected (mITTi) population. The mITTi population is defined as all patients randomized in the study who received any amount of study drug and had at least one positive SARS-CoV-2 RT-PCR test result *above or equal to the limit of quantification (LOQ)* during the study, with patients grouped according to the treatment assignment at randomization.

Safety analyses will be performed on the safety evaluable population, which consists of all patients who receive any amount of study drug. In all safety analyses, patients will be grouped according to the treatment that the patients actually received rather than the treatment assigned at randomization.

For *Cohorts A–D*, the primary virology analysis will be performed as part of a Day 10 review (accompanied with key safety review if deemed necessary, further details will be included in the SAP) which is to be completed after all patients enrolled in the current cohort have completed assessments through Day 10. Other endpoints will be analyzed at the completion of each full cohort or at the completion of the study.

For *Cohorts A–D*, all analyses at the Day 10 review or at the completion of each cohort will compare each AT-527 dose group and a combined placebo group, including all placebo patients enrolled across cohorts up to the cohort being analyzed, while analyses performed at the completion of the study will compare each AT-527 dose group and a combined placebo group from *Cohorts A–D*.

For *Cohort E*, the primary virology analysis will be performed as part of a Day 14 review (accompanied with key safety review if deemed necessary, further details will be included in the SAP) which is to be completed after all patients in *Cohort E* have completed assessments through Day 14. Other endpoints will be analyzed at the completion of the cohort.

For *Cohort E*, all analyses will compare the AT-527 dose group and the placebo group from *Cohort E* only. Data from cohorts with the same dose may be pooled to further evaluate the primary endpoint as part of a sensitivity analysis. Full details of all planned tables, listings, graphs, and statistical methods will be provided in a Statistical Analysis Plan (SAP), which will be finalized prior to the end of the study.

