6.4.2 Secondary Virology and Efficacy Endpoints

The following virology and efficacy secondary endpoints will be compared between each AT-527 dose group and the pooled placebo group *for Cohorts A–D and an unpooled placebo group for Cohort E*:

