5.3.3 Sensitivity Analyses for Primary Virology Endpoint

A sensitivity analysis may be performed, whereby only data obtained at the nominal timepoint is used. This means that the time windows in [Table 4](#) would not be applicable; only samples collected on the scheduled timepoints (Days 3, 5, and 7) would be included in the analysis.

At the end of the study, sensitivity analyses will also be performed for each cohort with a combined placebo group from all cohorts.

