5.4.2.2 Secondary Endpoints (Safety)

The safety objective for this study is to evaluate the safety of AT-527 compared with placebo.

The safety population will be used for all safety analyses. Patients will be analyzed according to the treatment they actually received.

Safety analyses will be presented by each AT-527 dose and a combined placebo group containing patients from all cohorts. Safety will be assessed through summaries of exposure to study treatment, AEs, changes in laboratory test results, and changes in vital signs and ECGs. If a low number of events is observed, a listing may be produced in place of a summary table. A listing of pregnancies will also be produced.

Study treatment exposure (such as treatment duration and total dose received) will be summarized with descriptive statistics.

- **Incidence and severity of AEs, with severity determined according to NCI CTCAE v5.0**

All verbatim AE terms will be mapped to Medical Dictionary for Regulatory Activities (MedDRA) thesaurus terms and will be classified by System Organ Class (SOC) and preferred term. AE severity will be graded according to NCI CTCAE v5.0. For AEs of varying severity, the highest grade will be used in the summaries. Deaths and cause of death will be listed.

Only treatment-emergent AEs will be summarized. Treatment-emergent AEs are defined as those AEs with observed or imputed onset date on or after the start date of trial treatment. Only where the most extreme intensity is greater than the initial intensity (or if most extreme intensity is not missing and initial intensity is missing) will events with an onset date prior to the start of study treatment be considered treatment-emergent.

An AE with a completely missing start date will be assumed to be treatment-emergent unless the AE has a complete non-imputed end date that is prior to study Day 1. AEs will be coded and tabulated by SOC and/or Preferred Terms (PTs). In tabulations, PTs

and their associated SOC will be presented in order of descending frequency summed across the treatment groups.

The following will be summarized for each AT-527 group and a pooled placebo group, and listings produced where required:

- AEs
- SAEs
- AEs related to study treatment
- AEs leading to death
- AEs leading to withdrawal of study drug
- AEs leading to withdrawal from study
- AEs occurring in $\geq 5\%$ of patients in at least one treatment group
- AEs occurring in $\geq 10\%$ of patients in at least one treatment group

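### The SAP was not updated for the version 6 redesign of Cohort E, so protocol and SAP define different end-of-study placebo comparators for Cohorts A–D

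*SAP*

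**What the plan says.** Protocol section 6 sets the rule for Cohorts A–D: "analyses performed at the completion of the study will compare each AT-527 dose group and a combined placebo group from *Cohorts A–D". For Cohort E it allows only that cohort's own placebo arm, apart from an optional sensitivity analysis of the primary endpoint that pools cohorts given the same dose. Section 6.4.2 repeats the split for secondary virology and efficacy endpoints, with pooled placebo "for Cohorts A–D and an unpooled placebo group for Cohort E", and section 6.5 does the same for safety.

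The SAP pools across all cohorts:

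- Section 5.1: "analyses performed at the completion of the study will compare each AT-527 dose group and a combined placebo group from all cohorts".
- Section 5.3.3, primary endpoint: "At the end of the study, sensitivity analyses will also be performed for each cohort with a combined placebo group from all cohorts".
- Section 5.4, secondary endpoints: each dose group is set against "a pooled placebo group containing patients from all cohorts".
- Section 5.4.2.2: "Safety analyses will be presented by each AT-527 dose and a combined placebo group containing patients from all cohorts".
- Sections 5.4.2.1 (the AUC endpoint), 5.4.2.3 and 5.6.1 use the full, all-available or all-cohort placebo group.

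SAP Appendix 1 says that nothing has changed from the analyses planned in the protocol. SAP sections 1.2, 1.2.1 and 3 still describe 220 patients in total and a Cohort E of 40 randomised 3:1. Protocol version 6 has 404 patients and a Cohort E of 224 randomised 1:1.

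**The concern.** Both rules are current text, and they cannot both be followed for the same tables.

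The choice matters because cohorts are enrolled one after another, and Cohort E is by design the last. Its placebo patients were not randomised against the active arms of Cohorts A–D. Protocol 3.3.3 justifies a placebo control on the ground that viral load falls anyway in the natural course of infection, and Protocol 1.1 describes changing variants and vaccine coverage. If the natural decline differs between enrolment periods, that difference enters the A–D contrasts. The ANCOVA in SAP 5.3.2 adjusts for baseline viral load but has no cohort term.

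Follow-up also differs: Cohort E has an in-person Day 14 visit with swab and vital signs, and Cohorts A–D have a telephone call.

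At stake are the end-of-study sensitivity analysis of the primary endpoint, the secondary virology and efficacy summaries with their 80% intervals, and the safety tables for the A–D doses.

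**Working it through.** **Inputs.** Protocol 6.1: Cohort A 60 at 1:1; Cohorts B–D 40 each at 3:1; Cohort E 224 at 1:1; 90% positive rate; SD 1.25 (Cohort E) and 1.2 to 1.85 (Cohorts A–D); one-sided alpha 10% for A–D. SAP 1.2 and 1.2.1: Cohort E 40 at 3:1.

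**Reproducing the plan's figures.**
- Totals: 60 + 3×40 + 224 = 404 (protocol); 60 + 4×40 = 220 (SAP).
- Cohort E power: 0.5 / (1.25√(2/100)) = 2.83; Φ(2.83 − 1.96) = 0.81. Then 100/0.90 = 111.1, rounded up to 112 per arm.
- Cohorts A–D power at 27 per arm: 0.7 with SD 1.2 gives 0.81, and 1.1 with SD 1.85 gives 0.82. Then 27/0.90 = 30 per arm.

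All agree with the documents.

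**Share of the control group from Cohort E.** Placebo in A–D is 30 + 10 + 10 + 10 = 60.

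| Rule and sizes | Placebo total | From Cohort E |
|---|---|---|
| Protocol rule | 60 | 0% |
| SAP rule, protocol version 6 sizes | 60 + 112 = 172 | 112/172 = 65% |
| SAP rule, SAP's own sizes | 60 + 10 = 70 | 10/70 = 14% |

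The 65% assumes full enrolment of A–D. It becomes 112/162 = 69% with A–C, 112/152 = 74% with A–B, and 112/142 = 79% with A alone.

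**Precision.** In the mITTi population at 90%, there are 27 active patients, 0.9×60 = 54 A–D placebo patients, and 54 + 100 = 154 from all cohorts. With SD 1.25:
- A–D placebo: 1.25√(1/27 + 1/54) = 0.295
- All cohorts: 1.25√(1/27 + 1/154) = 0.261
- Ratio: 0.295/0.261 = 1.13

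**Shift in the contrast.** Let d be the amount by which the mean decline in Cohort E placebo falls short of that in A–D placebo. The documents give no value; 0.2 to 0.5 log10 is assumed. The unadjusted contrast moves by (100/154)d = 0.65d in favour of the drug. A difference in the other direction hides an effect by the same amount.

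**False-positive rate, end-of-study sensitivity ANCOVA only.** Rate = 1 − Φ(1.2816 − 0.65d/SE).

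| d (log10) | Shift | Rate, SD 1.25 (SE 0.261) | Rate, SD 1.85 (SE 0.386) |
|---|---|---|---|
| 0.2 | 0.13 | 22% | 17% |
| 0.3 | 0.19 | 30% | 22% |
| 0.5 | 0.32 | 49% | 33% |

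The nominal rate is 10%. At the SAP's own sizes (9 of 63 mITTi placebo from Cohort E, SE 0.288 at SD 1.25), the same d values give 12%, 13% and 15%.

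**Adding a cohort factor to an all-cohort pool.** If each cohort tests a different dose, each contrast rests on that cohort's own placebo. In Cohorts B–D this is about 0.9×10 = 9 patients, and SE = 1.25√(1/27 + 1/9) = 0.48.

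**The case against.** The 65% puts the SAP's pooling rule on the protocol's Cohort E. In the design the SAP describes, the share is 14% and the effect is small. That stands as an explanation of how the conflict arose. It does not remove the problem, because protocol version 6 governs who is enrolled.

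A reader might infer that the sponsor deliberately reversed the protocol's choice of control. The documents do not show this. The SAP carries the smaller design throughout, with no Day 14 virology for Cohort E, which points to a document that was not updated.

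A reader might also infer that the main test of the primary endpoint in Cohorts A–D is compromised. It is not: SAP 5.1 and 5.3.2 run that test at the Day 10 review against placebo up to the cohort being analysed. The all-cohort pool is a sensitivity analysis for that endpoint. Secondary endpoints are descriptive with only optional testing, and the study is called hypothesis-generating.

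Third, the protocol's own pool is not purely concurrent. For Cohort A, 30 of 60 placebo patients (50%) come from other cohorts; for each of B–D it is 50 of 60 (83%). So it would be wrong to say that the protocol avoids non-concurrent controls. Cohort E may also start before the earlier cohorts finish, so some overlap is possible.

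Two mitigations deserve credit. The baseline covariate may absorb part of a shift between periods. SAP 5.7.3 plans baseline summaries of each cohort's placebo group, although it attaches no consequence to them.

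**Conclusion.** The point holds as a conflict between two current texts, caused by a SAP that lags protocol version 6. It should be corrected before the end-of-study analyses. Following the SAP at the planned version 6 sizes would make about two-thirds of the A–D control group Cohort E patients, against none under the protocol.

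Its reach is the end-of-study sensitivity analysis of the primary endpoint and the main descriptive comparisons for secondary endpoints and safety. The shift of 0.65d is conditional on an assumed d and on full enrolment. The 22% to 49% false-positive range further assumes SD 1.25 and no help from the baseline covariate, and it applies only to the end-of-study sensitivity ANCOVA. It should not be read as the error rate of any main analysis.

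**What to change.** In SAP 5.1, 5.3.3, 5.4, 5.4.2.1 to 5.4.2.3 and 5.6.1, define the end-of-study control for the Cohort A–D doses as the placebo patients of Cohorts A–D. Define the control for Cohort E as its own placebo patients, as Protocol 6, 6.4.2 and 6.5 require. Make the edit as part of bringing the SAP's description of Cohort E into line with version 6; changing the pooling phrases alone would leave the SAP describing a superseded Cohort E.

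This removes the added Cohort E exposure, not all use of non-concurrent placebo. The cost is wording plus the loss of precision shown above (SE 0.295 instead of 0.261).

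If an all-cohort pool is kept, label it supplementary and declare it with a reason in SAP Appendix 1. A cohort factor in that analysis would protect against period shifts, but it gives up most of the gain from pooling if each cohort tests a different dose (SE about 0.48 in Cohorts B–D).
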